3 OBJECTIVES AND OUTCOME MEASURES/ENDPOINTS

3.1 Primary objective

The primary objective of this study is to assess, in healthy volunteers, the effects of 3 regimens of aspirin (Aspirin lysine), or no aspirin, on the release of TNF- α during endotoxaemia.

It is hypothesised that TNF- α will be significantly lower when receiving aspirin 20 mg BD compared to 75 mg OD and 300 mg OD.

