10 STATISTICS AND DATA ANALYSIS

10.1 Sample size calculation

In our group's previous study of endotoxaemia in 30 participants receiving ticagrelor, clopidogrel or placebo, we saw, after log transformation, a mean 2 hour post-endotoxin plasma TNF- α 1.88 pg/ml with a standard deviation of 0.410 pg/ml.

There is no available raw data and no reliable estimate of the means or standard deviations of the log transformed TNF- α values for any of the three aspirin doses using the same methods. However, a study using a different endotoxin regimen has shown that aspirin 80 mg OD (which is not expected to be significantly different in effect to 75 mg OD) increased peak plasma TNF- α by around 40% compared to those receiving no drug.

We have a clear hypothesis that increasing aspirin dose increases TNF- α , therefore a one-sided test will suffice.

We estimate that clinically-relevant differences in plasma TNF- α at 2 hours post-endotoxin between the dosing regimens might be a 20% increase with 20 mg BD vs. no aspirin, 40% increase with 75 mg OD vs. no aspirin and 60% with 300 mg OD vs. no aspirin, based on the raw data.

These assumptions provide the following sample size estimate:

Test significance level, α	0.050
Number of groups, G	4
Variance of means, $V=S(m_i-m)^2 / G$	0.031
Common standard deviation, s	0.410
Effect size, $D^2 = V/s^2$	0.1828
Power (%)	80
n per group	16

Therefore, when the sample size in each of the 4 groups is 16, a one-way analysis of variance will have 80% power to detect at the 0.050 level a difference in means characterised by a Variance of means, $V=\sum(\mu_i-\mu)^2 / G$ of 0.031, assuming that the common standard deviation is 0.410.

To allow for up to 10% drop-out, the sample size per group will be 18. Drop-outs will not be replaced but it is expected that there will be at least 16 per group after withdrawals.

This sample size calculation was performed by [name] CStat, Senior Consultant, Statistical Services Unit, University of Sheffield, to whom the investigators are grateful.

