10.3.2 Primary outcome analysis

The primary endpoint will be plasma TNF- α at 2 hours following endotoxin administration assessed between aspirin groups (control vs. 20 mg BD vs. 75 mg OD vs. 300 mg OD, without ticagrelor) by one-way ANOVA with treatment as a factor.

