19. Bleeding time following endotoxin administration (measured at 0 and 3 hours post-endotoxin) compared between each aspirin regimen (control, 20 mg BD, 75 mg OD, 300 mg OD, each without ticagrelor) and each corresponding DAPT regimen (control, 20 mg BD, 75 mg OD, 300 mg OD, each with ticagrelor 90 mg BD) with a mixed three-way ANOVA with aspirin-dose and presence or absence of ticagrelor as between-subjects factors and timepoint as a within-subject factor.
20. Platelet aggregation to arachidonic acid (0.3 and 1 mmol/L), collagen (4 and 16 µg/ml) and ADP (20 µmol/L) over time following endotoxin administration (measured at 0 and 3 hours post-endotoxin) compared between each aspirin regimen (control, 20 mg BD, 75 mg OD, 300 mg OD, each without ticagrelor) and each corresponding DAPT regimen (control, 20 mg BD, 75 mg OD, 300 mg OD, each with ticagrelor 90 mg BD) with a mixed three-way ANOVA with aspirin-dose and presence or absence of ticagrelor as between-subjects factors and timepoint as a within-subject factor.

For all endpoints (primary and secondary) tested with ANOVA, pairwise comparisons with Bonferroni correction will be used to explore relationships further where the prespecified test suggests significant differences between the groups (p<0.05).

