18. Circulating leukocyte count over time following endotoxin administration (measured at 0, 0.5, 1, 1.5, 2, 3, 4 and 6 hours post-endotoxin) compared between each aspirin regimen (control, 20 mg BD, 75 mg OD, 300 mg OD, each without ticagrelor) and each corresponding DAPT regimen (control, 20 mg BD, 75 mg OD, 300 mg OD, each with ticagrelor 90 mg BD) with a mixed three-way ANOVA with aspirin-dose and presence or absence of ticagrelor as between-subjects factors and timepoint as a within-subject factor.

19. Bleeding time following endotoxin administration (measured at 0 and 3 hours post-endotoxin) compared between each aspirin regimen (control, 20 mg BD, 75 mg OD, 300 mg OD, each without ticagrelor) and each corresponding DAPT regimen (control, 20 mg BD, 75 mg OD, 300 mg OD, each with ticagrelor 90 mg BD) with a mixed three-way ANOVA with aspirin-dose and presence or absence of ticagrelor as between-subjects factors and timepoint as a within-subject factor.

20. Platelet aggregation to arachidonic acid (0.3 and 1 mmol/L), collagen (4 and 16 µg/ml) and ADP (20 µmol/L) over time following endotoxin administration (measured at 0 and 3 hours post-endotoxin) compared between each aspirin regimen (control, 20 mg BD, 75 mg OD, 300 mg OD, each without ticagrelor) and each corresponding DAPT regimen (control, 20 mg BD, 75 mg OD, 300 mg OD, each with ticagrelor 90 mg BD) with a mixed three-way ANOVA with aspirin-dose and presence or absence of ticagrelor as between-subjects factors and timepoint as a within-subject factor.

For all endpoints (primary and secondary) tested with ANOVA, pairwise comparisons with Bonferroni correction will be used to explore relationships further where the prespecified test suggests significant differences between the groups ( $p<0.05$ ).

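### For the four-group one-way ANOVAs, Shaffer's step-down would keep the same 5% familywise ceiling as the planned Bonferroni step and gain about 3 to 9 points of power per pair

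*Protocol*

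**What the plan says.** The primary analysis (Protocol and SAP, 10.3.2) compares TNF-α at 2 hours across four arms without ticagrelor, "by one-way ANOVA with treatment as a factor". The hypothesis in Protocol 3.1 is pairwise: TNF-α is expected to be lower on 20 mg BD "compared to 75 mg OD and 300 mg OD".

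The ANOVA alone cannot answer that. At the final analysis the pairwise answer comes from the last sentence of 10.3.3, which applies wherever an ANOVA is used, for the primary endpoint as well as the secondary ones. Its rule reads: "pairwise comparisons with Bonferroni correction will be used to explore relationships further where the prespecified test suggests significant differences between the groups (p<0.05". The SAP repeats it: "pairwise comparisons with Bonferroni correction will be used to explore relationships further where the prespecified test suggests significant differences between the groups". Neither document gives the divisor or restricts the pairs.

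Section 10.6 sets a different rule for the same endpoint at the interim: after a significant ANOVA, a fixed sequence of five pairs, each at p<0.05, without Bonferroni.

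**The concern.** The rule controls multiplicity twice. It requires the omnibus test to reject at 5%, and then divides 5% again by the number of pairs. With four groups and all pairs that means 0.05/6 = 0.0083 per comparison. The omnibus gate already covers the one situation in which all six pairwise nulls are true, so dividing by six behind it spends protection that the design no longer needs. At stake is power on the dose-against-dose comparisons, which are the content of the stated hypothesis, in a trial planned with 16 evaluable participants per group.

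**Working it through.** **Inputs (Protocol 10.1 unless stated).** Four groups, so 4 × 3 / 2 = 6 pairs (derived, not stated). Evaluable n = 16 per group; 18 randomised ("To allow for up to 10% drop-out, the sample size per group will be 18"). Common SD 0.410. Expected ratios to no aspirin: 1, 1.2, 1.4, 1.6. Pairwise tests are taken as two-sided t tests with the pooled ANOVA variance, 4 × (16 − 1) = 60 df. Section 10.1 calls a one-sided test sufficient, but the four-group F test has no direction.

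**The plan's own figure.** Natural-log means are 0, 0.1823, 0.3365 and 0.4700. Their variance (divisor 4) is V = 0.0307, so D² = V / 0.410² = 0.1828, as stated. The noncentrality is 4 × 16 × 0.1828 = 11.7, and the power of the 3 and 60 df F test is 80.2%. This reproduces the claim that "a one-way analysis of variance will have 80% power to detect at the 0.050 level". 16 / 0.9 = 17.8 gives 18.

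**How many pairwise nulls can be true.**

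| Pattern of four means | True pairwise nulls |
|---|---|
| all equal | 6 |
| three equal, one different | 3 |
| two equal pairs | 2 |
| one equal pair | 1 |
| all different | 0 |

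If all four are equal, the F gate alone limits any false claim to 5%. Otherwise at most three nulls are true. Shaffer's procedure behind the gate therefore orders the six p-values and compares them with 0.05/3 (first four), 0.05/2 and 0.05/1, stopping at the first failure.

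**Familywise error, simulated behind the F gate, n = 16.**

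| Pattern | Bonferroni, 0.05/6 | Shaffer step-down |
|---|---|---|
| all equal | 3.8% | 4.8% |
| three equal, one different | 2.2% | 4.4% |
| two equal pairs | 1.7% | 4.9% |
| one equal pair | 0.8% | 5.0% |

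**Power per pair behind the F gate, n = 16.** The critical t at 60 df falls from 2.73 (0.05/6) to 2.46 (0.05/3). The standard error of a difference is 0.410 × √(2/16) = 0.145, so the smallest log difference that can be declared falls from 2.73 × 0.145 = 0.396 to 2.46 × 0.145 = 0.357.

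| Pair | True log difference | 0.05/6 | 0.05/3 | Gain (points, before rounding) |
|---|---|---|---|---|
| 300 mg v none | 0.4700 | 68.9% | 74.3% | 5.4 |
| 75 mg v none | 0.3365 | 34.9% | 44.3% | 9.3 |
| 300 mg v 20 mg | 0.2877 | 23.9% | 32.1% | 8.2 |
| 20 mg v none | 0.1823 | 7.8% | 12.1% | 4.3 |
| 75 mg v 20 mg | 0.1542 | 5.4% | 8.7% | 3.3 |
| 300 mg v 75 mg | 0.1335 | 4.1% | 6.8% | 2.7 |

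The last two columns use a flat divisor of 3. The later steps of Shaffer's procedure can only add to this, and here they add almost nothing. At n = 18 the gains are 2.9 to 9.7 points.

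The chance of declaring at least one of the two hypothesised pairs rises from 25.7% to 34.5%; of declaring both, from 3.6% to 6.2%. Trials with a significant ANOVA but no significant pair fall from 80.2 − 75.3 = 4.9% to 80.2 − 79.5 = 0.7%.

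**Tukey for comparison.** The critical t is 2.64. Behind the gate it gains only 0.8 to 2.9 points over Bonferroni (75 mg v 20 mg 5.4% to 6.3%; 300 mg v 20 mg 23.8% to 26.4%).

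**The case against.** The planned rule is not an error. Bonferroni after an omnibus test is valid and conservative, and the sentence presents the comparisons as exploration after the primary ANOVA. That stands, and it makes this an efficiency point. It does not remove the point, because the sentence expressly covers the primary endpoint and Protocol 3.1 puts two of the pairs in the primary hypothesis.

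A reader might infer that the divisor of 3 can replace Bonferroni for every secondary ANOVA. The documents do not support that. In the first numbered list of 10.3.3, 12 of the 21 analyses (items 1, 3, 5–8, 12, 14, 16–19) are two-way mixed ANOVAs, and items 12–20 of the second list are three-way models over eight regimens. There the gate may open through time or an interaction, which does not protect a comparison of four equal treatment means. Six such pairs at 0.05/3 without an effective gate have a familywise error of 7.6%, against 4.0% at 0.05/6. Replacing the sentence outright would also leave the three-way models with no pairwise rule.

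The rule also bears only on a trial that reaches its planned final analysis. If the trial stops at the interim, 10.6 governs the primary endpoint by the fixed sequence and the other endpoints by mixed-effect linear models. This objection stands and limits the scope.

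**Conclusion.** A cheap improvement, confined to the four-group one-way ANOVAs (the primary, and items 2, 4, 9–11, 13, 15, 20 and 21 of the first list, counting item 20, which is labelled one-way mixed). For the primary endpoint at 16 per group, the same 5% ceiling can be kept with about 3 to 9 points more power per pair.

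Two stronger readings should be resisted. The ceiling is the same but the actual error is not: it rises from 3.8% to 4.8% with all means equal. Nor does the change rescue the hypothesis: 75 mg v 20 mg reaches about 9% and 300 mg v 20 mg about 32%, so the correction is not the main limit on power.

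The result assumes that Bonferroni means all six pairs, that tests are two-sided with pooled variance, and that effects and SD are on the natural-log scale. The last is inferred: natural logs reproduce V = 0.031, whereas log10 would give 0.0058, and the base of the SD is not stated. The error argument does not depend on the scale; the power figures do.

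**What to change.** Add to the closing rule of 10.3.3 in both documents: *For four-group one-way ANOVAs with a treatment-effect p<0.05, the six pairwise comparisons are tested by Shaffer's step-down procedure; Tukey's method is used where simultaneous intervals are wanted.*

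Keep the Bonferroni rule for the two-way and three-way mixed ANOVAs, and state its pairs and divisor. Reconcile the final pairwise rule for the primary endpoint with the fixed sequence in 10.6, so that it is clear which rule applies in which case.

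The cost is wording only, with no change to sample size or data collection. The downside is that confidence intervals matching a step-down test are less simple. Tukey's method avoids that but gives only about 1 to 3 points of the gain.

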10.4 Subgroup analyses

No pre-specified subgroup analyses are planned.

10.5 Adjusted analysis

If variables are found to be of skewed distribution, logarithmic transformation will be performed.

10.6 Interim analysis and criteria for the premature termination of the trial

After discussion between the investigators and the Sponsor, face-to-face participant study visits were halted on 17th March 2020 due to the unprecedented circumstances arising during the coronavirus disease 2019 (Covid-19) pandemic. It was considered by the investigators that the results of the study may have important implications for the management of cardiovascular disease patients who contracted Covid-19 in terms of optimal antiplatelet medication, in view of the morbidity and mortality in Covid-19 associated with dysregulated inflammatory response. It was noted that the recruitment and study activities to date had reached the level that had originally been planned for the study, as per the application funded by the British Heart Foundation. Given the uncertainty regarding restarting the trial, the need to preserve healthcare resources and to limit face-to-face encounters, the investigators and Sponsor decided that an interim analysis should be performed.

Sample size for interim analysis

Data from all participants who have completed visit 3 (first endotoxin day) will be included in the interim analysis. This is expected to include 46 participants who have completed visit 3, 37 of whom have completed the whole study giving a total of 83 endotoxin day visits, anticipated to be split into approximately equal numbers receiving each of the eight study treatment regimens.

Statistical procedure for interim analysis

The primary endpoint of the interim analysis will be plasma TNF- α measured at 2 hours after endotoxin administration assessed between aspirin treatment groups (control vs. 20 mg BD vs. 75 mg OD vs. 300 mg OD, without ticagrelor) using one-way ANOVA.

Should this demonstrate a significant difference between the groups ($p<0.05$), the following pre-specified pairwise comparisons will be performed, in hierarchical fashion:

300 mg OD vs. no aspirin

then, if significant ($p<0.05$)

75 mg OD vs. no aspirin

then, if significant ($p<0.05$)

300 mg OD vs 20 mg BD

then, if significant ($p<0.05$)

75 mg OD vs 20 mg BD

then, if significant ($p<0.05$)

20 mg BD vs no aspirin

Other analyses will be exploratory.

Criteria for premature termination

The trial shall be prematurely terminated if the primary interim analysis demonstrates a statistically significant ($p<0.05$) effect of aspirin dosing on plasma TNF- α two hours after endotoxin injection.

Additionally, continuing the study will be considered futile, and therefore discontinued, if the lower limit of the 95 % confidence interval of the mean change in TNF- α at 2 hours after endotoxin from the 300 mg aspirin OD group to no aspirin group is less than (more negative than) -2000 pg/mL.

Should neither of these criteria be met, the investigators will meet to review the results of the interim analysis and, in discussion with the Sponsor, decide on whether to continue the study, taking into account feasibility, including consideration of local and national restrictions.

Secondary analyses to be carried out in the event of premature termination

If the trial is prematurely terminated, data concerning other endpoints will then be analysed as follows, using methods taking best into account the cases of participant data missing from one period:

1. Plasma TNF- α over time following endotoxin administration (measured at 0, 0.5, 1, 1.5, 2, 3, 4 and 6 hours post-endotoxin) assessed between treatment groups (control vs. 20 mg BD vs. 75 mg OD vs. 300 mg OD, with or without ticagrelor) using a mixed effect linear model with patient as a random effect, aspirin dose, presence or absence of ticagrelor treatment and treatment period (first or second) as fixed effects, and baseline value as covariate.
2. Plasma IL-6 over time following endotoxin administration (measured at 0, 0.5, 1, 1.5, 2, 3, 4 and 6 hours post-endotoxin) assessed between treatment groups (control vs. 20 mg BD vs. 75 mg OD vs. 300 mg OD, with or without ticagrelor) using a mixed effect linear model with patient as a random effect, aspirin dose, presence or absence of ticagrelor treatment and treatment period (first or second) as fixed effects, and baseline value as covariate.
3. Change in serum CRP over time following endotoxin administration (measured at 0 and 6 hours post-endotoxin) assessed between treatment groups (control vs. 20 mg BD vs. 75 mg OD vs. 300 mg OD, with or without ticagrelor) using a mixed effect linear model with patient as a random effect, aspirin dose, presence or absence of ticagrelor treatment and treatment period (first or second) as fixed effects, and baseline value as covariate.
4. Serum TXB₂ over time following endotoxin administration (measured at 0, 0.5, 1, 1.5, 2, 3, 4 and 6 hours post-endotoxin) assessed between treatment groups (control vs. 20 mg BD vs. 75 mg OD vs. 300 mg OD, with or without ticagrelor) using a mixed effect linear model with patient as a random effect, aspirin dose, presence or absence of ticagrelor treatment and treatment period (first or second) as fixed effects, and baseline value as covariate.
5. Urinary PGI-M (measured at 0, 2, 4 and 6 hours, each adjusted for [divided by] urinary creatinine) over time following endotoxin administration, assessed between treatment groups (control vs. 20

mg BD vs. 75 mg OD vs. 300 mg OD, with or without ticagrelor) using a mixed effect linear model with patient as a random effect, aspirin dose, presence or absence of ticagrelor treatment and treatment period (first or second) as fixed effects, and baseline value as covariate.

6. Serum PGE₂ over time following endotoxin administration (measured at 0, 0.5, 1, 1.5, 2, 3, 4 and 6 hours post-endotoxin) assessed between treatment groups (control vs. 20 mg BD vs. 75 mg OD vs. 300 mg OD, with or without ticagrelor) using a mixed effect linear model with patient as a random effect, aspirin dose, presence or absence of ticagrelor treatment and treatment period (first or second) as fixed effects, and baseline value as covariate.
7. Circulating leukocyte count over time following endotoxin administration (measured at 0, 0.5, 1, 1.5, 2, 3, 4 and 6 hours post-endotoxin) assessed between treatment groups (control vs. 20 mg BD vs. 75 mg OD vs. 300 mg OD, with or without ticagrelor) using a mixed effect linear model with patient as a random effect, aspirin dose, presence or absence of ticagrelor treatment and treatment period (first or second) as fixed effects, and baseline values as covariate.
8. Bleeding time following endotoxin administration (measured at 0 and 3 hours post-endotoxin) assessed between treatment groups (control vs. 20 mg BD vs. 75 mg OD vs. 300 mg OD, with or without ticagrelor) using a mixed effect linear model with patient as a random effect, aspirin dose, presence or absence of ticagrelor treatment and treatment period (first or second) as fixed effects, and baseline values as covariate.
9. Platelet aggregation to arachidonic acid (0.3 and 1 mmol/L), collagen (4 and 16 µg/ml) and ADP (20 µmol/L) over time following endotoxin administration (measured at 0 and 6 hours post-endotoxin) assessed between treatment groups (control vs. 20 mg BD vs. 75 mg OD vs. 300 mg OD, with or without ticagrelor) using a mixed effect linear model with patient as a random effect, aspirin dose and presence or absence of ticagrelor treatment and treatment period as fixed effects, and baseline values as covariate.

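### The interim can stop the trial for efficacy at an unadjusted p<0.05 and the final test is again at 0.05, so overall type I error is not held at 5% and can reach about 8%

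*Protocol*

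**What the plan says.** Protocol section 10.1 sizes the trial for a single test. It states that with 16 per group "a one-way analysis of variance will have 80% power to detect at the 0.050 level a difference in means" of the size assumed. Allowing for 10% drop-out, this becomes 18 per group, 72 in all.

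Section 10.6, identical in the SAP, introduces an interim decided on after visits were halted in March 2020. It uses the same endpoint (TNF-α at 2 hours), the same four no-ticagrelor groups and the same one-way ANOVA. There are three outcomes:

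- **Efficacy.** "The trial shall be prematurely terminated if the primary interim analysis demonstrates a statistically significant" effect, with p<0.05 as the threshold.
- **Futility.** The study is to be discontinued if the lower 95% confidence limit for the change from 300 mg OD to no aspirin lies below -2000 pg/mL.
- **Otherwise.** "Should neither of these criteria be met, the investigators will meet to review the results of the interim analysis" and decide with the sponsor whether to go on, having regard to feasibility and restrictions.

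If the trial goes on, section 10.3.2 makes the final primary analysis the same ANOVA. That section names no significance level of its own. The level is read from 0.050 in section 10.1 and from the p<0.05 trigger for pairwise comparisons at the end of section 10.3.3. Neither document mentions alpha spending, a sequential boundary or a reduced final level, and section 10.9 (other statistical considerations) is marked not applicable.

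**The concern.** Testing accumulating data twice, each time at 0.05, gives two chances of a false positive. The interim alone uses the full 5%, and any final test adds to it. A claim from either look would then carry a nominal 5% that the procedure does not guarantee.

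This affects the primary test, and the setting gives little protection. The trial is open-label to investigators, has no formal data monitoring committee, and leaves the decision to continue with people who have seen the interim result. Section 10.6 also says that the findings may matter for antiplatelet choice in cardiovascular patients with Covid-19.

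**Working it through.** **Inputs.** Alpha 0.050, SD 0.410 on the log scale, increases of 20%, 40% and 60% over no aspirin, 16 evaluable and 18 enrolled per group (section 10.1). Interim: 46 participants with visit 3, 37 of them completers, 46 + 37 = 83 endotoxin visits, expected to split about evenly over eight regimens (section 10.6).

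**1. The plan's own figure.** The variance of ln(1, 1.2, 1.4, 1.6) is 0.0307, so D² = 0.0307/0.410² = 0.1828, as stated. The noncentrality is 64 × 0.1828 = 11.7 on 3 and 60 df, and power at 0.05 is 80.2% (77.1% with 15 per group). 16/0.90 = 17.8, rounded up to 18; 4 × 18 = 72. The single-look design reproduces.

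**2. Interim size.** 83/8 = 10.4 per regimen, so 41 or 42 in the four no-ticagrelor groups. Information fraction: 0.64 to 0.66 of 64, or 0.57 to 0.58 of 72.

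**3. Two looks at 0.05.** Overall error = P(p₁<0.05) + P(p₁≥0.05, trial continues, p₂<0.05). The first term is 5%. If the trial always continues, simulated null trials with nested F-tests (400,000 per case) give:

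| Interim | Final | Overall type I error |
|---|---|---|
| 10 per group | 16 per group | 8.1% |
| 10 per group | 18 per group | 8.4% |
| 11 per group | 16 per group | 7.9% |
| 11 per group | 18 per group | 8.2% |
| 41–42 in total | 64 in total | 8.0% |
| 41–42 in total | 72 in total | 8.3% |

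Repeated runs of the four equal-group cases agree to within about 0.2 points. Fractions from 0.51 (only the 37 completers, of 72) to 0.72 (46 of 64) give 8.5% to 7.7%. A two-sided 1-df normal approximation gives 7.8% and 8.1% for finals of 64 and 72. Section 10.1 also says "therefore a one-sided test will suffice", although the F-test has no direction; a one-sided 1-df version at 0.05 gives 7.5% and 7.8%.

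**4. When some second looks never happen.** If the trial continues in half of non-significant cases, irrespective of the data, the error is 5.0 + 0.5 × (7.8 to 8.4 − 5.0) = 6.4% to 6.7%. If it never continues, it is 5%.

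**5. The futility rule.** Its effect depends on the raw-scale SD, which the documents do not give. As an assumption range (normal raw data, 10 then 16 per group, no aspirin minus 300 mg OD):

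| Assumed raw SD (pg/mL) | Futility stops | Overall type I error |
|---|---|---|
| 1000 | about 1% | 8.0% |
| 2000 | 41% | 6.7% |
| 3000 | 69% | 6.1% |
| 4000 | 81% | 5.8% |

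The planning values (log mean 1.88, SD 0.410) imply a raw SD of about 142 pg/mL if the logs are base 10 and about 3 pg/mL if natural. On either, the rule would almost never act. A threshold of -2000 pg/mL may mean that much larger values were expected.

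**6. Levels that hold 5%.** O'Brien-Fleming-type spending at t = 10/16 = 0.625: interim level 2[1 − Φ(1.96/√0.625)] = 2[1 − Φ(2.48)] = 0.013. The final level, solved by simulation, is about 0.043 to 0.045. With equal levels, each look needs about 0.030 (0.029 to 0.032 over the fractions in step 3).

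**The case against.** A reader might infer that the trial's error rate simply is 8%. The documents do not support that. The 8% requires every non-significant interim to lead to a final test, while section 10.6 provides two other exits: a futility stop in mandatory words and a discretionary decision. Each removes a second look and pulls the rate towards 5%. This objection stands, and it makes 8% an upper figure. It does not remove the defect, because futility stops are conventionally given no credit when alpha is set, and continuation is expressly left open.

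It is also fair that the documents never claim an overall two-look rate of 5%. They give 0.050 for one ANOVA, and the final level has to be read across from sections 10.1 and 10.3.3.

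A reader might further infer that an early stop would be reported as confirmatory. The documents do not say so, and the protocol's section on trial committees calls the study exploratory. Against that, the plan has a primary hypothesis, a stated alpha and power, and a fixed pairwise sequence after which all other analyses are called exploratory. The primary test is thus set apart from the exploratory ones.

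Lastly, the hierarchical pairwise tests are already gated by the omnibus test and a fixed order. Nothing computed here shows that they must take the reduced interim level as well.

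**Conclusion.** Wrong as written. Two unadjusted looks at 0.05 do not hold the overall type I error at 0.050. It lies between 5% and about 8%, with the upper end (7.8% to 8.4% for 10 or 11, then 16 or 18, per group) reached if every non-significant interim goes on to a final test. Where it falls depends on how often futility or discretion ends the trial, and the documents cannot settle this without a raw-scale SD. The range rests on a final level of 0.05, a roughly even split of the 83 visits over the eight regimens, and a final size of 64 to 72.

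**What to change.** Amend section 10.6, and state the final level in section 10.3.2, in both documents. This must be fixed before the interim results are seen; the documents do not say whether they have been. Choose one:

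- **(a) Group-sequential boundary**, computed at the actual information fraction. One choice is O'Brien-Fleming-type spending: at 10 of 16 per group, stop for efficacy only if p<0.013 and test the final ANOVA at about 0.043 to 0.045. Equal levels of about 0.03 at each look also hold 5%; they make early stopping easier than 0.013 does, but leave a stricter final test.
- **(b) One confirmatory look.** Declare the interim the only confirmatory analysis and label later data exploratory. This needs no boundary.

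Lowering the final level alone does not work, because the interim at 0.05 has already spent the full 5%.

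The cost in text is a few lines. For the O'Brien-Fleming option under the planning assumptions (10 then 16 per group, SD 0.410), the chance of stopping early falls from about 56% to 34%, and overall power from about 82% with two unadjusted looks to 79%.

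### As literally written, the interim futility rule is inverted: it stops the trial when a large effect in the hypothesised direction is still plausible, and its 2000 pg/mL threshold is not derived

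*Protocol*

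**What the plan says.** Protocol 10.6, repeated in SAP 10.6, sets two stopping criteria for the interim analysis. The first ends the trial if the one-way ANOVA of 2-hour TNF-α across the four aspirin groups without ticagrelor gives p<0.05. The second is the futility rule: "continuing the study will be considered futile, and therefore discontinued, if the lower limit of the 95 % confidence interval of the mean change" in 2-hour TNF-α "from the 300 mg aspirin OD group to no aspirin group is less than (more negative than) -2000 pg/mL". Only if neither criterion is met do the investigators and sponsor have discretion over continuing.

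The expected direction is in protocol 10.1: "We have a clear hypothesis that increasing aspirin dose increases TNF"-α. The planned increases over no aspirin are 20% for 20 mg BD, 40% for 75 mg OD and "60% with 300 mg OD vs. no aspirin, based on the raw data". The planning mean and SD, described as log-transformed but with no log base given, are "1.88 pg/ml with a standard deviation of 0.410 pg/ml". Section 10.5 of both documents allows log transformation if a variable is skewed. Neither document gives a raw TNF-α level or says where 2000 pg/mL comes from.

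**The concern.** A change from one group to another is the second minus the first, here no aspirin minus 300 mg. If aspirin raises TNF-α, that difference is negative, and a larger effect pushes its lower limit further below −2000. A futility rule should fire when a worthwhile effect has been excluded. This one fires when such an effect remains compatible with the data.

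The rule is binding, concerns the primary endpoint, and operates in a trial without a formal data monitoring committee. At stake is a trial with a real but not yet significant effect being ended and labelled futile. The threshold is also in raw pg/mL although the design was planned on logs, so how often the rule could fire cannot be worked out from the plan.

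**Working it through.** **1. Reproduce the planning figure.** The planned ratios 1, 1.2, 1.4 and 1.6 have natural logs with variance V = 0.0307, so D² = 0.0307/0.410² = 0.1828, as printed. The noncentral F test (4 groups, α = 0.05) has power 0.802 at n = 16 and 0.771 at n = 15, so 16 per group is confirmed. On log10, V would be 0.0058. The effects were therefore planned on the natural-log scale, and 0.41 is used below as the natural-log SD.

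**2. Direction.** Literal contrast = no aspirin − 300 mg. With no-aspirin mean M and a 60% rise, its expected value is M − 1.6M = −0.6M. The rule fires if (observed difference − half-width) < −2000. The first term becomes more negative as the effect grows, so the probability of firing rises with the effect.

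**3. Firing rates.** Protocol 10.6 expects 83 endotoxin visits over eight regimens: 83/8 = 10.4, taken as 10 per group. Simulation used lognormal data, natural-log SD 0.41 and the pooled 95% t-interval. M is an assumed arithmetic mean. The value 6550 is what the planning mean would imply if the assay unit were ng/mL, which the documents do not say.

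| Assumed M (pg/mL) | Literal rule fires, no effect | Literal rule fires, planned +60% |
|---|---|---|
| 76 | 0% | 0% |
| 2000 | 1% | 62% |
| 3000 | 10% | 94% |
| 6550 | 64% | 99.9% |

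**4. Net of the efficacy stop.** With all four groups at their planned ratios and 10 per group, the ANOVA gives p<0.05 in about 50% of trials (raw values) to 56% (log values). Trials stopped by the literal futility rule but not by the efficacy rule are about 18–21% at 2000 pg/mL and 38–44% at 3000.

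**5. The opposite contrast.** For 300 mg − no aspirin, firing falls as the effect grows: about 10% (no effect) v 0.3% (planned) at 3000 pg/mL, and 64% v 6% at 6550. With no effect, the rise from 10% to 64% comes only from a wider raw-scale interval.

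**6. Scale.** exp(1.88) = 6.55 and 10^1.88 = 75.9 pg/mL. A 60% rise is then about 3.9 or 45.5 pg/mL; 2000 is about 509 or 44 times that. With zero observed difference and 10 per group, the lower limit reaches −2000 only if the raw SD is 2000/(2.10 × √(2/10)) ≈ 2130 pg/mL; the back-transformed planning SD is about 3 (natural log) or 142 (log10). A 60% rise equals 2000 pg/mL only if M = 2000/0.6 ≈ 3333, a figure found in neither document.

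**7. A correctly directed rule.** Stop if the upper 95% limit of the log ratio (300 mg/no aspirin) is below ln 1.6 = 0.470. SE = 0.41 × √(2/10) = 0.183 and t(36) = 2.03, so the half-width is 0.372 and the observed log ratio must be below 0.098. P(stop) is Φ(0.098/0.183) ≈ 0.70 with no effect and Φ(−2.03) ≈ 0.02 with a true ratio of 1.6; simulation gives 2–3%. By the same formula it is about 0.32 at a true ratio of 1.2 and 0.10 at 1.4.

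**The case against.** The strongest reply is that the sentence is loosely worded rather than wrong. The same section lists its pairwise comparison as 300 mg against no aspirin. If that order was meant, the rule fires more often without an effect than with one, and at 6550 pg/mL its performance (64% v 6%) approaches that of the rule in step 7. This stands in part: on that reading the direction is not inverted. It does not make the rule sound. It still looks at the limit farthest from the hypothesised effect, so a wide interval can trigger it while a large increase remains plausible. A binding rule should not admit two readings with opposite behaviour.

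Second, a reader might infer from the 94% that the rule would wrongly stop nearly every successful trial. The documents do not support that: the p<0.05 criterion already ends about half of planned-effect trials at the interim, and only the net figures in step 4 measure the harm.

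Third, a reader might infer that −2000 pg/mL can never be reached. That is too firm, because the log base is not stated and raw units are attached to a logged value. The supportable statement is that sections 10.1 and 10.6 cannot be reconciled as printed. The two faults also bite in different settings: at the printed planning mean the rule is practically inert, and the inversion matters only if TNF-α runs to thousands of pg/mL.

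**Conclusion.** The concern holds for the sentence as literally written. The inversion follows from the text alone, given the stated hypothesis. Its size depends on a no-aspirin level that the documents do not give. At assumed means of 2000 to 3000 pg/mL, with 10 per group and natural-log SD 0.41, about 18–21% to 38–44% of trials with the planned effect would be wrongly ended after allowing for the efficacy stop. At the printed planning mean the rule would practically never fire. On the opposite sign it is correctly directed but depends on precision. On no reading is the threshold derived from the planned effect. Because the rule is binding on the primary endpoint, it should be corrected before it is applied.

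**What to change.** In section 10.6 of the protocol and the SAP, replace the futility sentence with one that states the contrast, the confidence limit and the scale. Suggested wording: futility is declared only if the upper 95% confidence limit of the geometric mean ratio of 2-hour TNF-α (300 mg OD over no aspirin), from log-transformed values, lies below a pre-stated worthwhile ratio. With the planned 1.6 as that ratio, about 70% of no-effect trials and 2–3% of planned-effect trials would stop. The margin is the sponsor's choice; because 1.6 would also stop about 32% of trials with a true ratio of 1.2 and 10% at 1.4, a smaller ratio or a conditional-power rule may be preferred.

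If the raw scale is kept, reverse the inequality so that the lower limit of no aspirin minus 300 mg must be less negative than the threshold, and derive the threshold from the expected no-aspirin level. In either case, state the log base and units in protocol 10.1 and reconcile them with 10.6.

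The cost is one sentence in each document and a clarification in 10.1. No extra participants or data are needed.
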